6.3 Special Instructions and Definitions of Evaluations

6.3.1 Documentation of HIV infected status at screening

The lack of HIV-1 infection will be documented by any licensed screening antibody (rapid test plus NAT or Ab/Ag) test. A positive HIV test will be confirmed by a second EIA , Western Blot, or HIV RNA viral load.

6.3.2 Medical and Laboratory History

At screening, a medical history will be obtained and will be recorded in the source documents. The medical history should include any previous illnesses that might be consistent with acute HIV infection, history of STI and other routine medical conditions.

6.3.3 Medication History

At screening, a medication history (only of those taken within the last 30 days prior to entry) with actual or estimated start and stop dates will be obtained and recorded in the source documents and the concomitant medication CRF, including:

- ◆ All prescription medications.
- ◆ Non-prescription medications.
- ◆ Alternative therapies and/or dietary supplements.
- ◆ Allergies to any medications and their formulations must be documented.

6.3.4 Concomitant Medications

During study visits all antibiotics and other concomitant medications taken since the last visit will be recorded in the source documentation and entered into the concomitant medication log CRF.

6.3.5 Study Drug Modifications

No modifications of PrEP regimen will be allowed on this study. TDF/FTC may be temporarily held for adverse events as per section 7. TDF/FTC should be discontinued if any criteria for stopping are met (see discontinuation section). Discontinuation will be documented on the TDF/FTC discontinuation CRF.

6.3.6 Clinical Assessments

Targeted Physical Exam

A targeted physical examination will be based on any signs or symptoms previously identified that the subject has experienced within 30 days of entry or since the last visit. This examination will be performed at all visits when indicated. Documentation must include any symptoms consistent

with acute HIV infection.

Height and Weight

Height and weight will be measured at study entry.

Signs and Symptoms

All signs, symptoms, toxicities and deaths will be documented in the subject's record. At entry, all signs/symptoms experienced within 30 days of entry will be recorded on the CRFs. For all other visits including a suspected HIV infection visit, all Grade > 1 signs and symptoms will be recorded on the CRFs that have occurred since the last visit. Any signs or symptoms that lead to a change in treatment, regardless of Grade, will be recorded on the CRF. The source document will include date of onset and date of resolution, but the CRF will only record prevalence of a given adverse event since the previous study visit.

Refer to the ACTG Table for Grading Adult Adverse Experiences.

Diagnoses

The following should be recorded on the CRFs: HIV and STI diagnoses, malignancies, new medical conditions and death. The source document must include date of diagnosis and date of resolution.

6.3.7 Clinical Assessments for Detected STI

At all visits ask if the participants if they have had an STI in the interim, current symptoms.

6.3.8 Laboratory Evaluations

Record all designated laboratory values on the CRFs throughout the course of the study. All baseline values, regardless of toxicity, for specific laboratories will also be recorded on the laboratory CRF including: WBC, neutrophil count, hemoglobin, platelets, creatinine with estimated GFR (Cockcroft-Galt formula), glucose, AST/ALT, alkaline phosphatase and total bilirubin. All values of creatinine with estimated GFR (Cockcroft-Galt Formula) will be recorded in the CRF and performed as per the SOE.

Any laboratory toxicities that lead to a change in treatment, regardless of Grade, will be recorded on the adverse event CRF.

Refer to the Division of AIDS Table for Grading Adult Adverse Experiences.

6.3.9 Urinalysis
A dipstick urine test will be done at screening and every visit after day 0. Protein, glucose and leukocyte esterase will be recorded in the CRF.

6.3.10 T-cell counts and Virology tests

Plasma HIV-1 RNA

An HIV-1 RNA viral load will be performed at the site's local laboratory within 7 days of a new positive antibody test or NAT.

An HIV drug resistance test should be performed with detectable viral load of greater than 500 copies/mL.

CD4 T-cell enumeration will be performed to obtain absolute CD4+/CD8+ count and percentages within 7 days of new HIV diagnosis.

6.3.11 *Stored Plasma and other specimens*

Stored plasma will be collected at day 0, at all visits and with any new HIV diagnosis.

*Specimens will be stored at the site's local laboratory and batched shipped to the central laboratory (UCSD) after completion of the study.

6.3.12 *Pharmacokinetic Studies*

At each visit, record the time and date of the last 3 doses of TDF/FTC medication in the CRF. Dried blood spots will be stored at -80 at each visit beginning at Week 12 for possible future use for plasma and intracellular TFV and FTC pharmacology.

6.3.13 *Questionnaires*

At each visit, the subject should complete the self-reported questionnaires.

6.3.14 *Rectal swabs*

At day 0 and at one additional time point on or after Week 48, all subjects will have a rectal swab stored for possible future studies of the gut microbiome. These tests will be done in retrospect and not available for the subjects.

6.3.15 At day 0, all subjects will have blood stored for future use to examine host DNA. Subjects will sign a consent that informs them of the storage of material for possible host genomic testing.

6.3.16 Participants will be asked to recall food items eaten over the last 3 days at the week 36 visit. The calculator used in the ACTG 5280 study, which is adopted from the USDA database, will be used to quantify vitamin D and calcium intake (see Appendix VI).

6.4 Schedule of Evaluations for Subjects On-Study, Off-Medications

6.4.1 At any point, subjects may elect to stop study medications but remain on study. Subjects that stay on study but stop medications will not be allowed to resume again.

Subjects will follow the same schedule as defined in Section 6.1 until the end of study. Study medications will not be dispensed at clinic visits, and evaluations related to counseling or monitoring of medications (including urine dipstick and serum creatinine) will not be performed. These include Adherence and Risk-reduction counseling and collection of dried blood spots. If the subject was randomized to the iTab arm, their account will be switched to “inactive.”

STI and HIV rapid test screenings and questionnaires will still be administered as the schedule dictates.

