4.0 SELECTION AND ENROLLMENT OF SUBJECTS

4.1 Main Study Inclusion Criteria

- 4.1.1 Man or transgender M to F who has sex with men.
- 4.1.2 Age 18 years or older.
- 4.1.3 Subjects must have substantial ongoing risk of acquisition of HIV as evident by one or more of the following:
 - ♦ Has at least one HIV infected sexual partner for ≥ 4 weeks.
 - ♦ No condom use during anal intercourse with ≥ 3 male sex partners who are HIV-positive or of unknown HIV status during the last 3 months
 - ♦ No condom use during anal sex with ≥ 1 male partner and STI diagnosis during the last 3 months
- 4.1.4 Negative for HIV infection by rapid HIV test and confirmed negative by NAT or other sensitive method such as antibody- antigen test.
- 4.1.5 Acceptable laboratory values in the past 30 days:
 - ♦ Calculated creatinine clearance of at least 60 mL/min by the Cockcroft-Gault formula (eCcr (male) in mL/min = $[(140 - \text{age in years}) \times (\text{lean body weight in kg})] / (72 \times \text{serum creatinine in mg/dL})$)
 - ♦ Alanine aminotransferase (ALT) and/ or aspartate aminotransferase (AST) < 3 x upper limit of normal (ULN)

- ◆ Hemoglobin > 9 g/dL
- ◆ Absolute neutrophil count > 750/ mm³
- ◆ Platelets > 75,000/ mm³

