In the standard study visit, the coordinator will perform HIV testing and blood work, review test results, provide TDF/FTC prescriptions, discuss medication use, adherence, risk reduction and troubleshoot any barriers. The standard behavioral survey will include assessment of TDF/FTC adherence, HIV transmission risk behaviors, substance use, depression scores and other risk behavior details (e.g. sexual partnerships, sexual acts, condom use).

Laboratory Safety Assessments

At follow-up clinic visits, all participants will have a blood drawn for creatinine clearance estimates. A rapid test for HIV will be performed. HIV test results will be provided during the clinic visit. If there are grade 3-4 adverse events (thought to be related to study medication- see toxicity section) or HIV seroconversion is detected, the participant will be called to discontinue TDF/FTC and to come to the clinic as soon as feasible. Any positive rapid test will be confirmed by Western Blot and HIV RNA; CD4 cell count and an HIV genotype for drug resistance will be done. Newly diagnosed HIV subjects will be counseled and be linked to HIV clinical care within the existing clinic or to another provider

designated by the participant. All PrEP-related clinic visits, laboratory testing and TDF/FTC medication will be provided by the study without charge to the subject.

FTC Qualitative Plasma Concentration as an Adherence Marker:

Plasma will be drawn at every visit starting at week 4 for FTC concentrations. Samples will not be run in real time and will not be available for clinical use.

Chlamydia, gonorrhea and syphilis testing

Subjects will have day 0 and every 24-week assessment to include urine and swabs from the rectum and throat for NAT testing for Chlamydia and gonorrhea. Blood will be drawn for RPR. In between visits, subjects will be told to come to the study nurse if they experience symptoms of an STI. They will also be asked if they were tested elsewhere between visits. All new STI cases will be referred to their provider or the Department of Health for treatment. They will be given a card to have filled out documenting treatment given, which they will be asked to bring back to their next study visit. All new STI cases will also be counseled on the need for partner therapy and will suggest that they receive assessment and treatment or partner delivered therapy. STI testing can also occur as an interim visit for high-risk exposure or symptoms suggestive of new STI.

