Sexual Risk Counseling

Standard of care HIV risk reduction counseling will be providing to all participants consistent with pre- and post-test counseling for persons receiving community HIV testing. The study will provide streamlined in-person risk reduction counseling at each visit that will use the RESPECT paradigm of focusing on a single risk behavior as identified by the subject. The goal of brief and targeted counseling is to help the individual to identify his most significant risky behavior and to implement concrete actions to decrease the specific risk behavior until the next study visit. Participants will undergo this process at each visit.

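### Section 6.4.1 withdraws scheduled sexual risk-reduction counselling from subjects who elect to stop study drug but stay on study, although rapid HIV testing continues at the same visits

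*Combined protocol and SAP*

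**What the plan says.** Section 6.4.1 provides that "At any point, subjects may elect to stop study medications but remain on study". These subjects keep the section 6.1 visit schedule to the end of the study, and "Subjects that stay on study but stop medications will not be allowed to resume again".

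The section then stops evaluations connected with counselling about, or monitoring of, the medication. Urine dipstick and serum creatinine are given as examples, and the text adds: "These include Adherence and Risk-reduction counseling and collection of dried blood spots". What remains is stated in its last sentence: "STI and HIV rapid test screenings and questionnaires will still be administered as the schedule dictates".

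Section 6.2.3, under Sexual Risk Counseling, describes risk-reduction counselling as "consistent with pre- and post-test counseling for persons receiving community HIV testing", to be given to every participant at every visit. Its stated purpose is behavioural: "The goal of brief and targeted counseling is to help the individual to identify his most significant risky behavior". Under Laboratory Safety Assessments, the same section says that "HIV test results will be provided during the clinic visit".

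**The concern.** Most items dropped by 6.4.1 follow from stopping the drug. Adherence counselling, dipstick, creatinine and dried blood spots all serve drug taking, drug safety or drug levels. Risk-reduction counselling, as 6.2.3 describes it, concerns sexual behaviour, and the need for it does not end when the tablets do.

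The subjects concerned entered under section 4.1.3: "Subjects must have substantial ongoing risk of acquisition of HIV as evident by one or more of the following". Once they elect to stop, they have no study PrEP and may not restart it. They still attend, are still tested for HIV and are still given the result, but the scheduled risk-counselling session at that visit is withdrawn. What is at stake is a modest protection for participants, not the validity of the main comparison.

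**Working it through.** The plan states no figure on this point. The check is a comparison of text, followed by a count of scheduled sessions.

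**Step 1. Does the item fit the stated reason?** Section 6.4.1 gives medication-related evaluation as its reason. Section 6.2.3 describes risk-reduction counselling by sexual behaviour and makes no mention of the drug. The item is named in 6.4.1, so the lead-in cannot be read as covering medication counselling only.

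**Step 2. Do testing and counselling fall at the same visits?** In the section 6.1 table, the risk-reduction counselling row and the rapid HIV test row are marked at the same on-study visits: week 0 and every follow-up visit. Every scheduled session lost is therefore at a visit where the rapid test is still done.

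**Step 3. Count the sessions.** Inputs from section 6.1: weeks 0, 4, 12, 24, 36 and 48 make 6 sessions by week 48. Weeks 60, 72, 84 and 96 add 4, making 10 by week 96, the maximum follow-up in section 5.1.3.

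Formula: share lost = (scheduled sessions after stopping) / (all scheduled sessions in follow-up).

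| Drug stopped | Follow-up to week 48 | Follow-up to week 96 |
|---|---|---|
| Before week 4 | 5/6 = 83% | 9/10 = 90% |
| After week 4, before 12 | 4/6 = 67% | 8/10 = 80% |
| After week 12, before 24 | 3/6 = 50% | 7/10 = 70% |
| After week 24, before 36 | 2/6 = 33% | 6/10 = 60% |
| After week 36, before 48 | 1/6 = 17% | 5/10 = 50% |

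The counts assume that every visit is attended. They leave out any separate end-of-study visit; if there is one, it adds one session to both the top and the bottom of each fraction.

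**Step 4. Is the primary endpoint touched?** Section 9.1 requires the subject to be on study medication through week 48. Stopping earlier already fails the endpoint, and stopping later comes after it is measured. The 6.4.1 rule is the same in both arms.

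**The case against.** The strongest reply is that this is a choice the protocol was free to make, with no demonstrated consequence. Several parts of that reply stand.

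- **It is not a contradiction.** A reader might infer that 6.4.1 conflicts with the promise in 6.2.3 of counselling for all at each visit. But 6.4.1 is a specific exception for a defined group, and sites can follow it as written.
- **Subjects are not left without any counselling.** A reader might infer that off-drug subjects are tested with no counselling at all. The documents do not support that. Section 3.1 lists routine HIV testing and counselling as part of visits in both arms. Section 6.2.3 provides counselling for new HIV diagnoses and on partner therapy for new STI cases. Section 6.4.1 does not expressly withdraw any of these. The 6.1 table also marks risk-reduction counselling at suspected-infection and interim visits, and it is unclear whether 6.4.1 reaches those.
- **Continued high risk is not shown.** Section 4.1.3 describes risk at entry. Some subjects may stop because their risk has fallen, and PrEP outside the study is not barred. Against this, objective 1.2.4 separates perceived from actual risk, and the adherence questionnaire in Appendix II offers having sex without feeling at risk as a reason for not taking PrEP. Stopping is therefore not evidence of low risk either.
- **The reach is limited.** A reader might extend the rule to subjects stopped for toxicity, whom section 7.1 follows on study but off drug. Only the heading of 6.4 suggests this. The text speaks of those who elect to stop, and its ban on resuming does not fit section 7, which allows some restarts.

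None of this gives a reason for placing sexual-risk counselling among the medication-related items.

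**Conclusion.** The point holds as a minor matter of participant care. For subjects who elect to stop drug and stay on study, 6.4.1 removes the scheduled risk-reduction session while rapid HIV testing continues at the same visits, and its stated reason does not cover that session.

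The loss per subject runs from 83% to 90% of scheduled sessions for the earliest stoppers, down to 17% to 50% for those stopping between weeks 36 and 48. The upper figures need full attendance to week 96, and under section 8.1.8 one missed visit after week 48 ends participation. The documents do not say how many subjects will stop and stay, and they give no basis for converting lost sessions into infections or risk behaviour. A reader might infer a bias in the primary comparison, but section 9.1 rules that out.

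**What to change.** In section 6.4.1, delete the words 'and Risk-reduction' from the sentence listing stopped items, so that it names only adherence counselling and dried blood spots. In the last sentence of 6.4.1, insert 'risk-reduction counseling' between the rapid-test screenings and the questionnaires. Subjects already off drug restart the sessions at their next scheduled visit. Adherence counselling, dipstick, creatinine and dried blood spots stay dropped.

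The cost is a few minutes of existing staff time per visit (an assumption; 6.2.3 describes the counselling as brief) and IRB review of the modification under section 12.1. No new visit, assay or CRF is needed.

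The one analytic cost is that off-drug subjects would be counselled differently before and after the amendment. This bears on HIV seroconversion (1.2.5), STI acquisition (1.2.6) and risk behaviour (1.2.7). It is probably small but cannot be sized from the documents, so the amendment date should be reported with those results.

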6.5 End of Study Visit and Post-study 3-month Follow-up

6.5.1 At the End of Study (EOS) visit, subjects will be asked to complete additional questionnaires in addition to completing regular procedures. These surveys will assess subjects’ experiences over the course of the study including changes in their medical insurance status, access to other health services, changes in their perceptions of PrEP and of their own health, and their opinions on the intervention.

Upon completion, subjects will not be dispensed PrEP and will be discontinued from the study.

Subjects that express the desire to continue PrEP after completing the study will be provided information regarding access and payment strategies.

- 6.5.2 Subjects that complete CCTG 595 will be approached EOS and asked to join a supplement-funded extension, consisting of a one-time phone call follow-up scheduled for 3 months post-study. The purpose of this extension is to examine sexual risk compensation and the impact of transition after cessation of study-provided PrEP.

Written consent will be obtained at EOS; subjects that have already completed their EOS visit will be contacted and verbal consent will be obtained over the phone.

At 3 months post-study, subjects will be contacted over the phone and asked questions regarding their current HIV status, their ability to access and maintain their PrEP regimen after EOS, and their ability to obtain health insurance coverage. If subject is off PrEP and/or has no health insurance, the subject will be asked for their reasons and possible barriers. Subjects will also be asked an abbreviated number of questions from surveys similar to those done during the main study, including measures assessing risk compensation, perceptions of PrEP efficacy, and adherence (if on PrEP).

7.0 TOXICITY MANAGEMENT

The management of medication related toxicities should be undertaken by the local investigators, with guidance available from the protocol team, protocol pharmacist and pharmaceutical sponsor, to ensure the optimal safety and efficacy for the individual subject.

7.1 General Management for Grade 1-4 Events

7.1.1 Grade 1 or 2

Subjects who develop a Grade 1 or 2 adverse event or toxicity may continue TDF/FTC without alteration of the dosage, except as noted below. Persistent grade 1 or 2 toxicity should be discussed with the protocol team. Those subjects experiencing Grades 1 or 2 adverse events which results in discontinuation of the TDF/FTC should continue to be followed on study, but off study medication.

7.1.2 Grade 3

Management of Grade 3 toxicities should be discussed with the protocol team via email. Please refer to the subsequent sections for management of specific events.

In the event that a subject develops a **symptomatic** Grade 3 reaction considered to be TDF/FTC-related, the study drug should be discontinued and the subject should be followed weekly until resolution of the adverse event. Once Grade 3 is resolved the subject should be followed on-study, but off study medication. For subjects with asymptomatic Grade 3 toxicity or laboratory abnormalities, the protocol team should be consulted for possible re-introduction of TDF/ FTC.

7.1.3 Grade 4

Subjects who develop a Grade 4 adverse event or toxicity judged to be TDF/ FTC-related will have the study drug permanently discontinued. For other Grade 4 events, if the toxicity or laboratory elevation is thought not to be due to TDF/FTC, TDF/FTC may be continued and laboratories repeated within 2 weeks (for example for asymptomatic elevation of CPK or triglycerides). If it is not possible for the investigator to discern another causative agent/ condition or if TDF/FTC could be the causative agent, then TDF/FTC must be discontinued. Subjects experiencing Grade 4 adverse events requiring permanent discontinuation of TDF/FTC therapy should be followed weekly until resolution of the adverse event. Once Grade 4 is resolved the subject should be followed on-study, but off study medication.

7.2 Management for Specific Adverse Events

7.2.1 Rash

Grade 1 or 2

TDF/FTC may be continued without interruption. Subjects with a Grade 1 or 2 rash may be treated symptomatically with permitted antipyretic, antihistamine and/or non-steroidal anti-inflammatory medications, but should be monitored closely by the local investigator.

Grade 3 or 4

Grade 3 or 4 rash necessitates that TDF/FTC be held unless the rash is determined to be unrelated to TDF/FTC. The rash should be followed closely for resolution and the subject followed on-study, off study medication.

7.2.2 Nausea and Vomiting

Grade 1 or 2

TDF/FTC may be continued without interruption. Subjects with Grade 1 and 2 nausea or vomiting may be treated symptomatically with permitted oral antiemetic therapies or antiemetic suppositories. Subjects will be instructed to take medications with food.

Grade 3 or 4

Subjects with Grade 3 TDF/FTC-related nausea and vomiting should interrupt TDF/FTC until the toxicity grade returns to Grade ≤ 2 or to baseline and be treated symptomatically. After discussion with the protocol team and if the subject is willing, the TDF/FTC may be resumed when symptoms have resolved. If Grade 3 nausea and vomiting recurs upon the resumption of TDF/FTC despite symptomatic treatment, TDF/FTC should be discontinued. Grade 4 nausea or vomiting will lead to permanent discontinuation of drug. Once resolved, the subject should be followed on-study, but off study drug.

